Sample size. Our sample size is calculated based on estimated differences of intervention effects between two arms on the primary outcome: CAPS total score at 4 months, or treatment end. The CAPS total score is a continuous measure (0-136) and reflects a combined score reflecting symptom frequency and symptom severity. A recently published yoga pilot study for patients with PTSD⁹ found a pre-treatment CAPS score of 77.33 (standard deviation = 28.6). Post-treatment scores were reduced by 34% (CAPS = 51.1, SD = 27.6, effect size = 0.9) from the yoga intervention. We powered on a medium effect size of 0.55 which requires a larger sample size than 0.9. We recognize the correlation of outcomes from subjects within the same yoga class may reduce the effective sample size compared to the same sample with independent observations. This possible “clustering effect” has implications for power. Randomization will occur at the individual not cluster or clinic level. Also, we expect that the intra-cluster correlation (ICC) will be near zero because groups will have a mixture of participants from the various recruitment sites: therefore, there is no reason to believe that participants within groups would be more correlated on the outcomes than participants from different groups. We have no preliminary data to estimate the intra-cluster correlation (ICC) for participants within the same group. However, based on similarly designed published studies, we expect the ICC to be relatively small and balanced across the two treatment arms since the cluster sizes will be similar. We will assume an ICC of 0.05 for both groups. We will also assume a 20% difference between treatment groups. The absolute score difference at 4 months is estimated to be approximately 15.4 points (61.6, 80% of 77). Assuming a common standard deviation of 28 and using a two-sample t-test, we will need 60 evaluable subjects in each arm to detect such a difference (Cohen’s $d = 0.55$) with >85% power and 5% Type I error rate. With approximately 8 subjects per treatment group/class session or cluster, the design effect is $1 + (8-1) \times 0.05 = 1.35$. Therefore, we will inflate our sample size by 35% to accommodate the potential clustering effects. We then need 81 evaluable subjects in each arm. With an assumed 30% attrition, we will then need $(81 \times 2) / 0.70 = 232$ subjects (116 in each arm).

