Data analysis: Baseline characteristics of the RELIEVE sample. To evaluate representativeness, we will compare enrollees and those who decline enrollment on baseline characteristics (socio-demographic variables, psychiatric comorbidity, and current and prior PTSD treatments). Any differences will be considered when interpreting results of subsequent analyses. We will also examine differences in baseline characteristics between patients who remain in the study and those who dropout. The linear mixed modeling approach (see next section) will ensure that all available data are used for subjects who have missing data. The models will also incorporate dropout status to adjust for follow-up missing data pattern. All participants will have baseline data. The possible missing data patterns will be (1) missing 4 month, not 7 month, (2) missing 7 month, not 4 month, (3) missing both 4 and 7 months, and (4) complete data.

Main analysis of the primary outcome. Our main analysis will use the ANCOVA (analysis of covariance) approach to linear mixed modeling of repeated measures in which the baseline measure of the relevant outcome scores (i.e., CAPS or PCL) is adjusted as a covariate in the model.⁸⁵ The model for CAPS will be adjusted for baseline CAPS score. The model for PCL, a continuous measure with a possible range of 17-85, will be adjusted for baseline PCL score. The CAPS and PCL are measured at every time point (baseline, 8 weeks, 4 months, 7 months) except the CAPS is not administered at 6 weeks in order to reduce participant burden, since the CAPS and PCL are highly correlated. We plan an intent-to-treat analysis with the primary endpoint at 4 months and evaluation of “early” response at 8 weeks and “sustained” response at 7 months (3 months post-intervention). The models will simultaneously incorporate three post-baseline measures (8 weeks ([PCL only], 4 months, and 7 months) of the relevant response variable. The main predictors will be group (treatment arm), time (categorical with indicator variables to avoid restrictive assumption of linearity over time), and their interaction. A random intercept will be used to adjust for the potential clustering effect for patients in

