a specific yoga group. And a subject-specific random intercept (nested within the group effect) will accommodate the correlation among repeated measurements from the same patient. Aim 1 will involve testing intervention effects by using the appropriate contrast from the model to test the difference in CAPS score and PCL score between the two treatment arms at 8 weeks (early response), 4 months (the primary end point which occurs immediately post intervention), and 7 months (sustained effect of intervention). Descriptive statistics including adjusted means, SD, and effect sizes (differences between two arms on adjusted means divided by pooled SD) will be reported for outcomes at each time point. Variables that are either known, or shown with our data, to be significantly correlated to the outcomes, will be considered as covariates, irrespective of their degree of baseline imbalance between randomized groups (e.g., combat vs. con-combat PTSD, baseline credibility score, and mTBI).

Secondary analysis of primary outcome. For the CAPS and PCL total scores, we will also report a clinically relevant descriptive statistic in which we define the patients with more than 30% reduction from baseline as “responders.” We will then compare the probability of responders between treatment arms using a generalized linear mixed model with a logit link. The responding status of each patient at 8 weeks (for PCL only), 4 months and 7 months will be used as the outcome variables. Main predictors are group (treatment arm), time (8 weeks for PCL only, 4 months and 7 months) and their interaction. A significant coefficient of group indicates a significant odds ratio of being a responder between the two arms.

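### The random-intercept model pools one residual variance across visits, so if the baseline correlation decays the 7-month standard errors are too small and the earlier ones (4-month CAPS, 8-week PCL) too large

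*Combined protocol and SAP*

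**What the plan says.** All of this is in the combined protocol and SAP, section 8.0 Statistical Considerations.

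- **Baseline.** The main analysis is an ANCOVA-type mixed model "in which the baseline measure of the relevant outcome scores (i.e., CAPS or PCL) is adjusted as a covariate in the model". The other fixed effects are arm, categorical time and their interaction. No baseline-by-time term is named.
- **Within-patient correlation.** Beside a random intercept for class, "a subject-specific random intercept (nested within the group effect) will accommodate the correlation among repeated measurements from the same patient". The section names no unstructured covariance, visit-specific residual variance or robust standard error.
- **Visits modelled.** CAPS at 4 and 7 months; PCL at 8 weeks, 4 months and 7 months.
- **Claims.** Aim 1 takes a separate arm contrast at each visit: early response, primary endpoint (4 months) and sustained effect (7 months). The secondary outcomes use the same modelling approach.
- **Missing data.** The multiple-imputation sensitivity analysis again uses linear mixed models, with no change of covariance structure stated.
- **Sample size.** It rests on CAPS at 4 months: "The absolute score difference at 4 months is estimated to be approximately 15.4 points". The SD is taken as 28 in both arms and the test is an unadjusted t-test. On that basis the plan states: "we will need 60 evaluable subjects in each arm to detect such a difference". Power is put at more than 85% for a Type I error of 5%.

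**The concern.** A subject random intercept with homogeneous residuals implies the same residual variance at every post-baseline visit. With three visits (PCL) it also implies one common correlation between visits. If baseline predicts the later visits less well, the variance left after baseline adjustment grows with time. The model averages it and uses the average for every contrast. The early contrast is then judged against too large a standard error and the late one against too small a standard error.

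What is at stake is mainly the 7-month contrast, which carries the claim that any benefit lasts. Its false-positive rate would exceed the nominal 5%, while some precision is given away at the primary visit. Time is made categorical to avoid assuming linearity, but the baseline slope and the residual variance are held constant over time.

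**Working it through.** **1. The plan's own figure.** Inputs: difference 15.4, SD 28, alpha 0.05 (two-sided assumed; the plan does not say), power 85%.

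- n per arm = 2 × 28² × (1.96 + 1.036)² / 15.4² = 59.4, rounded up to 60. Power at 60 per arm is 85.4% by the normal approximation (84.8% by noncentral t).
- 60 × 1.35 = 81: "We then need 81 evaluable subjects in each arm".
- "With an assumed 30% attrition", 162 / 0.70 = 231.4, rounded up to 232.

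The sample size reproduces. It comes from a t-test without covariates, so nothing below changes it.

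**2. What the model does with complete data.** Let r_j be the correlation of baseline with visit j, s_j the SD at visit j and s_0 the baseline SD.

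- Fitted common slope: b = mean over visits of r_j s_j / s_0.
- True residual variance at visit j: v_j = s_j² − 2 b r_j s_j s_0 + b² s_0².
- Variance used at every visit: the mean of the v_j.
- SE ratio (model/true) = √(mean v / v_j). Actual Type I error = 2 × [1 − Φ(1.96 × ratio)].

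**3. CAPS.** The correlations are assumed, because the documents give none. SD is 28 at baseline and both visits. The effective sample is 81 / 1.35 = 60 per arm, so SE = √(2v/60).

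| r at 4 / 7 mo | b | v at 4 / 7 mo | mean v | model SE | true SE 4 / 7 mo | ratio 4 / 7 mo | Type I 4 / 7 mo |
|---|---|---|---|---|---|---|---|
| 0.50 / 0.50 | 0.50 | 588.0 / 588.0 | 588.0 | 4.43 | 4.43 / 4.43 | 1.00 / 1.00 | 5.0% / 5.0% |
| 0.65 / 0.55 | 0.60 | 454.7 / 548.8 | 501.8 | 4.09 | 3.89 / 4.28 | 1.05 / 0.96 | 4.0% / 6.1% |
| 0.60 / 0.40 | 0.50 | 509.6 / 666.4 | 588.0 | 4.43 | 4.12 / 4.71 | 1.07 / 0.94 | 3.5% / 6.6% |
| 0.70 / 0.40 | 0.55 | 417.5 / 676.2 | 546.8 | 4.27 | 3.73 / 4.75 | 1.14 / 0.90 | 2.5% / 7.8% |

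The last row is a sharper decay, shown for range.

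**4. PCL, 0.75/0.65/0.55 (assumed), equal SDs.** b = 0.65. In units of the SD squared, v = 0.4475, 0.5775 and 0.7075, with mean 0.5775. Ratios are 1.14, 1.00 and 0.90. Type I error is 2.6%, 5.0% and 7.7% at 8 weeks, 4 months and 7 months.

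**5. Power at the primary endpoint.** As planned: Φ[(15.4 − 1.96 × model SE) / true SE]. With visit-specific slope and variance: Φ[15.4 / SE − 1.96], where SE = √(2 × 28² × (1 − r²) / 60).

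- 0.65/0.55: (15.4 − 8.02) / 3.89 gives 97.1% as planned; SE 3.885 gives 97.7% with the fix.
- 0.60/0.40: (15.4 − 8.68) / 4.12 gives 94.9% as planned; SE 4.09 gives 96.5% with the fix.

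**6. When the error cancels.** For two visits the v_j are equal when s_7 / s_4 = √[(1 − r_4²) / (1 − r_7²)].

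- 0.65/0.55: √(0.5775 / 0.6975) = 0.91, a 7-month SD 9% lower.
- 0.60/0.40: √(0.64 / 0.84) = 0.87, a 7-month SD 13% lower.

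**7. Simulation check.** Compound-symmetry REML fits, 232 patients, 8,000 null trials per setting. At CAPS 0.60/0.40, Type I error was 3.6% and 6.3% with complete data, and 3.4% and 7.1% with 20%/30% random dropout at 4/7 months. In a smaller simulation (1,500 trials per setting, Monte Carlo error about 0.6 points), unstructured covariance with baseline-by-visit terms gave 5.0 to 5.4% under the same dropout, at 0.65/0.55 and at 0.60/0.40.

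Neither the formulas nor the simulations include the class random intercept.

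**The case against.** The strongest reply is that the problem is conditional and small, and spares the primary endpoint. Much of that stands. The documents give neither the correlations nor a 7-month SD. Equal values produce no error, and a somewhat lower 7-month SD would cancel or reverse it. The plan is also silent on residual structure, and a random intercept does not rule out visit-specific residual variances. Homogeneous residuals are only the usual default.

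Four stronger readings are tempting but unsupported:

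- **That the primary test has an inflated false-positive rate.** Under decay with equal SDs, the 4-month CAPS test is conservative.
- **That power falls below target.** Applying an SE excess of 5 to 15% to the unadjusted t-test figure of 84.8% would suggest 82 to 77%. But the SE error arises only because baseline is adjusted for, and that adjustment first raises power well above 85%. The 15% excess also needs a 7-month SD about 15% larger. Nothing in the documents supports that: the plan assumes a common SD of 28, and the cited pilot's pre- and post-treatment SDs are 28.6 and 27.6.
- **That a common correlation is wrongly imposed on CAPS.** Two post-baseline visits have only one correlation. For CAPS only the equal-variance constraint can do harm; for PCL both constraints apply.
- **That the plan considered this and judged it negligible.** Its remark about a small intra-cluster correlation concerns classes, not repeated measures.

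What survives is that the plan makes a separate claim at each visit from a model whose standard errors are right at each visit only if the residual variances happen to match.

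**Conclusion.** The concern holds in conditional form, as a low-cost improvement and not a flaw in the primary test. It rests on four assumptions: homogeneous residuals, a baseline correlation that falls between visits, roughly equal SDs across visits, and no class effect in the calculation.

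For the two moderate CAPS settings, the primary 4-month contrast loses about 0.6 to 1.6 points of power and stays above 94%. The material effect is on the 7-month contrast, whose false-positive rate is about 6 to 7% against a nominal 5%. PCL is affected at both ends (conservative at 8 weeks, liberal at 7 months) and almost untouched at 4 months.

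**What to change.** In the main-analysis paragraph of section 8.0:

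- Replace the subject random intercept with an unstructured within-participant covariance across the post-baseline visits.
- Add a baseline-by-visit term. This alone would not be enough, because the variance would still be pooled.
- Use Kenward-Roger or Satterthwaite degrees of freedom.
- Keep the class random intercept.
- Pre-specify a fallback for non-convergence, for example variances allowed to differ by visit.
- Carry the same specification over to the secondary outcomes.

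Cost: SAP wording only. CAPS gains 2 parameters (covariance 2 to 3, slopes 1 to 2). PCL gains 6 (covariance 2 to 6, slopes 1 to 3). With about 162 evaluable participants planned, that is small. The remaining downside is a small risk of non-convergence, which the fallback covers. Sample size, visits and data collection do not change, and almost nothing is lost if the correlation does not decay.

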Missing data.⁸⁷ Based on our prior studies, we anticipate a possible dropout rate of 30%, which is reflected in the sample size calculation. We will first run a logistic model with missing status as the response variable, intervention arm, patients’ demographic characteristics as covariates, to check whether the missing status depends on the intervention group assignment and patient characteristics. Second, our linear mixed effects model can accommodate missing-at-random (or MAR which is assumed in many trials) where no bias will be introduced by ignoring the missing-data mechanism. If drop-outs are Missing Not At Random (MNAR), meaning the likelihood of drop-out depends on an un-observed outcome, and the missing data mechanism is ignored, potential bias can be introduced. We will run sensitivity analyses using linear mixed models with the “multiple imputation” method and 100 generated data sets to compare results with the standard linear mixed effects modeling without imputation to assess the robustness of the inference.

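### The responder analysis uses observed status only and the planned imputation does not reach it, so crude response rates cover only patients with a score and the CAPS model loses patients missing both follow-ups

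*Combined protocol and SAP*

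**What the plan says.** All statistical text is in Section 8.0 of the combined protocol and SAP.

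- **Responder definition and model** (Secondary analysis of primary outcome). A responder has "more than 30% reduction from baseline" on CAPS or PCL. "We will then compare the probability of responders between treatment arms using a generalized linear mixed model with a logit link". The outcome is described as follows: "The responding status of each patient at 8 weeks (for PCL only), 4 months and 7 months will be used as the outcome variables". The main predictors listed are arm, time and their interaction. Baseline score and 8-week PCL are not among them.
- **Expected loss** (Missing data). "we anticipate a possible dropout rate of 30%, which is reflected in the sample size calculation".
- **Handling of missing data** (Missing data). The missing-at-random statement is made for the linear mixed effects model. The imputation is worded: "We will run sensitivity analyses using linear mixed models with the “multiple imputation” method and 100 generated data sets".
- **Foreseen patterns** (Data analysis: Baseline characteristics). The plan lists patients missing 4 months only, 7 months only, both, or neither. It also says the models will include dropout status, directly after a sentence about linear mixed modelling.
- **Schedule** (Section 5.0, Outcome Assessment Protocol table). CAPS is given at screening, 4 months and 7 months. PCL is given at baseline, 8 weeks, 4 months and 7 months. The main-analysis paragraph of Section 8.0 justifies omitting the early CAPS by the strong correlation between the two scales.

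**The concern.** The responder comparison is how the plan intends to express the primary outcome in clinical terms. Nothing says how a patient without a score is classified or which denominator the reported rate uses, so the default is patients with a score at that visit. If leaving is linked to early progress, those rates differ from the rates among all randomised patients. If the link differs between arms, the odds ratio is distorted as well.

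CAPS is the more exposed scale. A patient missing both 4 and 7 months supplies no row to the CAPS responder model, and a dropout indicator cannot help where there is no outcome to attach it to. That patient's baseline CAPS and any 8-week PCL carry information about likely response, and the model as described does not use it.

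**Working it through.** **1. The plan's own figures.** The inputs are "The absolute score difference at 4 months is estimated to be approximately 15.4 points (61.6, 80% of 77", then "Assuming a common standard deviation of 28 and using a two-sample t-test, we will need 60 evaluable subjects in each arm", "with >85% power and 5% Type I error rate". Sidedness is not stated, so two-sided is assumed.

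- d = 15.4/28 = 0.55; n = 2(1.960 + 1.036)²/0.55² = 59.4, so 60 per arm.
- Design effect 1 + 7 × 0.05 = 1.35; 60 × 1.35 = 81 per arm.
- (81 × 2)/0.70 = 231.4, so 232, or 116 per arm.

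The sample size reproduces. It implies about 116 − 81 = 35 patients per arm (70 in total) without an evaluable 4-month score.

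**2. True response under stated assumptions.** The plan gives no response rates. From the plan: baseline CAPS 77, SD 28, benefit 15.4. Assumed: the control arm falls 10%, and the baseline to 4-month correlation is 0.5.

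- Control 4-month mean 77 × 0.9 = 69.3; yoga 69.3 − 15.4 = 53.9; threshold at the mean baseline 0.7 × 77 = 53.9.
- SD of (4-month score − 0.7 × baseline) = 28 × √(1 + 0.49 − 2 × 0.7 × 0.5) = 28 × √0.79 = 24.9.
- Control: Φ(−(69.3 − 53.9)/24.9) = Φ(−0.62) = 27%. Yoga: Φ(0) = 50%.
- Odds ratio (0.50/0.50)/(0.27/0.73) = 2.7.

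**3. Crude observed 4-month CAPS rates with 30% dropout.** These are by simulation. Further assumptions: 8-week to 4-month correlation 0.7, baseline to 8-week correlation 0.5, half the mean change reached by 8 weeks, and a logit dropout slope of 0.8 per SD of 8-week change. Ranges reflect repeat runs with slightly different settings.

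| Dropout mechanism | Control | Yoga | OR |
|---|---|---|---|
| None (truth) | 27% | 50–51% | 2.7 |
| Unrelated to progress | 27% | 50% | 2.7 |
| Poor early responders leave both arms | 31% | 56% | 2.8 |
| Poor early responders leave yoga only | 27% | 56% | 3.4 |
| Opposite by arm (poor leave yoga, good leave control) | 23% | 55–56% | 4.2–4.4 |
| Opposite, reversed | – | – | 1.8 |

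In the opposite-by-arm case the risk difference is about 33 points against a true 23. The standard error is √(2 × 0.45 × 0.55/81 × 1.35) = 0.091, so the error is about one standard error.

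**4. What the mixed model recovers.** A random-intercept logistic model was simulated with 8,000 patients per arm under separate assumed rates.

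- 31% missing at 7 months only, depending on observed 4-month status and arm: truth 30.0% vs 45.9%; crude 31.9% vs 51.1%; model 29.8% vs 45.7%; log odds ratio 0.98 (true 1.0). The model recovers the randomised population.
- 30% missing both visits, depending on latent response and arm: truth 29.5% vs 47.0%; model 32.0% vs 53.7%; log odds ratio 1.23 (true 1.0). The model follows the patients who stayed.

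A PCL-type model with an 8-week score for every dropout, under the step 3 assumptions, gave about 25% vs 53% and OR 3.3–3.5 in the opposite-by-arm case. In the equal-arms case it gave 29–30% vs 53–54% and OR 2.8.

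**5. Imputing first.** Imputing the score by arm from baseline and 8-week data and then applying the 30% rule restores 27% vs 50% (OR 2.7) if every dropout gave an 8-week score. If only half did, the opposite-by-arm case gives about 25% vs 52% (OR 3.2).

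**The case against.** A reader might infer that both the response rates and the odds ratio describe completers only. The documents do not support that for the odds ratio. The planned model is a mixed model on repeated statuses, so it keeps anyone with at least one observed visit: in the PCL model, dropouts who gave an 8-week score; in the CAPS model, patients missing only one of the two visits. Step 4 shows it can recover the full-population result when missingness depends on observed status.

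A reader might also take the 30% to mean that about 70 patients lack both 4- and 7-month scores. It is an anticipated overall dropout rate, and the plan does not split it by pattern.

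Other points on that side also have weight. The plan has phone and mail back-up for missed assessments (Section 5.0) and a logistic model of missingness on arm and patient characteristics, although early progress is not among the listed predictors. Whether the dropout-status adjustment extends to the responder model is unclear. The intent-to-treat statement is in the main-analysis paragraph, so the responder text is silent on the analysis population and does not contradict it. The analysis is secondary. A material shift in the odds ratio needs dropout that works differently in the two arms.

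Three things remain: no rule or denominator for missing status, imputation tied to a different class of model, and no contribution from CAPS patients missing both visits.

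**Conclusion.** The concern holds in limited form. Crude response rates describe patients with a score at the visit, and the CAPS responder model drops those missing both follow-ups although informative data on them may exist. With 30% dropout tied to poor early progress equally in both arms, crude 4-month CAPS response is about 4 to 5 points too high per arm and the odds ratio barely moves (2.8 against 2.7). Mechanisms that differ by arm move it to about 1.8 to 4.4 at the extremes. Dropout unrelated to progress produces no bias.

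These sizes rest on the assumed control change, correlations and dropout slope, none of which the documents give. They apply to crude rates and to CAPS patients missing both visits, and they overstate the problem for the PCL model. The primary comparison of continuous CAPS at 4 months and the sample size of 232 are unaffected. The change should be made before unblinding, because the choice of rule can move the result.

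**What to change.** In Section 8.0, Secondary analysis of primary outcome:

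- Derive responder status by applying the 30% rule to the CAPS and PCL scores in the 100 imputed data sets already planned.
- Impute by arm, using baseline CAPS and PCL and all available 8-week, 4-month and 7-month scores.
- Combine results by Rubin's rules and report proportions for all randomised patients in each arm (116 planned).
- Keep the observed-data logit mixed model as supportive.

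Counting missing as non-response is optional and suits only a sensitivity analysis, because it has its own bias when dropout differs by arm. If observed rates were 50% vs 30% (OR 2.33), it gives 0.6 × 50% = 30% vs 0.8 × 30% = 24% (OR 1.36) with 40% yoga and 20% control dropout. With the split reversed it gives 40% vs 18% (OR 3.04).

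The cost is a few sentences and light programming. The downsides are that the result depends on the imputation model, that bias is only partly removed when dropouts lack an 8-week PCL, and that the reported rates may be less favourable than observed-only rates.

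### The responder model does not state adjustment for the baseline score, leaving its odds ratio open to bias if dropout depends on baseline differently by arm

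*Combined protocol and SAP*

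**What the plan says.** All references are to section 8.0 of the combined protocol and SAP.

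- **Main analysis of the primary outcome.** A repeated-measures linear mixed model with the baseline score as covariate: "The model for CAPS will be adjusted for baseline CAPS score". A matching sentence covers PCL.
- **Secondary analysis of primary outcome.** A participant whose CAPS or PCL total falls by over 30% from baseline is a responder. Response is compared between arms in a logit-link mixed model: "Main predictors are group (treatment arm), time (8 weeks for PCL only, 4 months and 7 months) and their interaction". The paragraph names no baseline covariate and does not refer back to the main model. The secondary-outcomes paragraph, by contrast, does refer back.
- **Missing data.** The plan expects 30% dropout and argues that "our linear mixed effects model can accommodate missing-at-random". The multiple-imputation sensitivity analysis is likewise for linear mixed models. The responder model is not mentioned.

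**The concern.** Response is defined relative to baseline, but that alone does not make the chance of response independent of baseline. When the baseline-to-follow-up correlation is modest, people who start high regress more and cross the 30% threshold more often.

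A participant with no follow-up contributes nothing to the responder model. If dropout is related to baseline in one arm but not the other, or in opposite directions, the people left in the two arms differ in baseline and so in their chance of response. The main model conditions on baseline and is protected against that pattern; a responder model without baseline is not. The two analyses could then disagree only because of who left. The plan offers the responder comparison as its clinically relevant reading of the primary outcome and tests it for significance.

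**Working it through.** **1. The plan's own figure.** Inputs from the sample size paragraph: "The absolute score difference at 4 months is estimated to be approximately 15.4 points (61.6, 80% of 77"; "Assuming a common standard deviation of 28"; "with >85% power and 5% Type I error rate". Sidedness is not stated; two-sided is assumed.

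- Effect size: 15.4/28 = 0.55.
- n per arm = 2(1.960 + 1.036)² × 28²/15.4² = 59.4, so 60. The plan agrees: "we will need 60 evaluable subjects in each arm to detect such a difference".
- Clustering: 60 × 1.35 = 81. Attrition: 162/0.70 = 231.4, so 232.

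The total of 232 reproduces. The plan gives no power or sample size for the responder analysis, so this point does not touch it.

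**2. When baseline predicts response.** Baseline CAPS is taken from the pilot: the plan says that study "found a pre-treatment CAPS score of 77.33 (standard deviation = 28.6". The correlation r between baseline and 4-month CAPS is not given; 0.3, 0.5 and 0.7 are assumed. With follow-up SD 28, expected follow-up rises by r × 28/28.6 per baseline point, while the response threshold rises by 0.7. The margin for response therefore changes per baseline point by 0.7 − 0.979r:

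| r | 0.7 − 0.979r | Simulated response OR per baseline SD (no effect, WLP mean 77) |
|---|---|---|
| 0.3 | 0.406 | 1.88 |
| 0.5 | 0.210 | 1.45 |
| 0.7 | 0.015 | 1.04 |

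At r = 0.7 baseline barely predicts response. The crossing point is 0.7/0.979 = 0.715; correlations above 0.7 were not simulated.

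**3. Bias under assumed dropout.** Setup: 400,000 simulated subjects per setting; baseline restricted to 30–136 (an assumption); follow-up kept within 0–136; response if follow-up is below 0.7 × baseline. Dropout is logistic in standardised baseline, with the intercept set to give 30% in each arm. A dropout OR of 2 per SD then means about 16% dropout at 1 SD below the mean and 44% at 1 SD above. Ranges cover WLP follow-up means of 77 and 65. There is no true effect:

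| Dropout OR per baseline SD (HYP / WLP) | r = 0.3, without / with baseline | r = 0.5, without / with | r = 0.7, without / with |
|---|---|---|---|
| 2 / 1 | 0.89–0.90 / 1.01 | 0.93–0.94 / 0.99–1.02 | 1.00–1.01 / 1.00–1.02 |
| 2 / 0.5 | 0.80–0.81 / 1.01 | 0.87–0.88 / 1.00 | 0.99–1.00 / 1.00–1.02 |
| 2 / 2 | 1.01 / 1.01 | 0.99–1.01 / 0.99–1.01 | 1.00 / 1.00 |

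Reversing the dropout pattern between the arms reverses the direction of the bias. If percent reduction is unrelated to baseline, the OR stays at 1.00 even under the 2 / 0.5 pattern.

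**4. With the planned effect.** For a 15.4-point benefit (WLP mean 77) and the 2 / 0.5 pattern, the unadjusted OR falls from 2.43 in full data to 1.95 at r = 0.3, from 2.86 to 2.50 at 0.5, and from 3.74 to 3.71 at 0.7. The adjusted OR hardly moves: 2.60 to 2.61, 2.94 to 2.93 and 3.74 to 3.76.

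**5. Type I error and power.** 1,500 trials of 116 per arm, WLP mean 70. Percentages are without / with baseline:

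| | r = 0.3 | r = 0.5 | r = 0.7 |
|---|---|---|---|
| Type I error, 2 / 0.5 pattern | 9.3 / 4.2 | 6.4 / 4.9 | 4.5 / 4.3 |
| Power, 2 / 0.5 pattern | 53.7 / 77.2 | 77.5 / 86.5 | 96.1 / 95.6 |
| Power, dropout unrelated to baseline | 75.0 / 77.4 | 85.8 / 86.9 | 97.4 / 97.3 |

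The simulation standard error is about 0.75 points at 9.3% (√(0.093 × 0.907/1500)). In a similar simulation with one-arm dependence of OR 2, type I error without baseline was 5.8% at r = 0.3 and 5.6% at r = 0.5.

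The simulations use a single time point. Class clustering and repeated measures were left out.

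**The case against.** **The list may not be complete.** The main model's own list of main predictors also stops at group, time and their interaction, although that model contains baseline. The responder paragraph also leaves its random effects unstated, so it is plainly abbreviated. A reader might infer that baseline is deliberately excluded; the documents do not support that. What stands is that the main model states the adjustment separately and the responder model never does. The sentence on considering outcome-correlated covariates is discretionary, sits in the main-analysis section and does not give the baseline score as an example. The sentence on incorporating dropout status follows the one on linear mixed models and does not name the responder model.

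**The bias needs two conditions that the documents do not supply.** Baseline must predict response, and dropout must depend on baseline differently by arm. A reader might infer that the responder result will be biased. No passage gives dropout by arm or by severity, or the correlation. Opposite dependence by arm is a strong assumption; under one-arm dependence type I error stays close to 5%. Steeper patterns give larger figures, but nothing in the plan points to them.

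**Adjusted and unadjusted odds ratios are different quantities.** A reader might take the whole gap between them as bias. With full data at r = 0.3 they are already 2.60 and 2.43, because the odds ratio is non-collapsible. The like-for-like comparisons in step 4 avoid this.

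**The stakes are limited.** The plan labels this a secondary analysis and a descriptive statistic, and claims missing-at-random protection only for the linear model, so it does not contradict itself.

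**Conclusion.** The point holds as a gap in specification with a conditional consequence. The plan does not put the baseline score in the responder model, and its stated missing-data protection does not extend to that model.

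Under assumed one-arm dependence (dropout OR 2 per baseline SD) and no true effect, the unadjusted OR is about 0.90 at a correlation of 0.3 and 0.93 at 0.5. Under opposite dependence it is about 0.8 and 0.9, with type I error of about 9–10% and 6–7%. Adding baseline brings the OR back to about 1.0. The bias essentially disappears at a correlation of 0.7 or with equal dependence in both arms.

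A reader might also infer a material loss of power from the omission alone. Without differential dropout the gain from adding baseline is only about 0 to 3 points. The primary 4-month CAPS test and the total of 232 are unaffected. This is a minor improvement to a secondary analysis.

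**What to change.** In the secondary analysis of the primary outcome (section 8.0), add one sentence: the responder model includes the baseline total of the same scale (CAPS for CAPS response, PCL for PCL response) as a continuous covariate, as in the main model, and the odds ratio is reported as conditional on baseline.

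The cost is that sentence and the change in what the odds ratio means. The plan says every participant will have baseline data, so nothing new is collected. In the scenarios above, adjustment introduced no bias and cost at most about half a point of power (96.1% to 95.6%), which is within simulation error.
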